Surrogate decision-makers will be assessed pre-intervention/baseline (Time point 1, T1), post-intervention (within a week of the surrogate decision-maker's completion of the baseline assessment) (Time point 2, T2), 1-months after post-intervention assessment (Time point 3, T3), and 3-months after post-intervention assessment with an additional exit interview with the research staff that will take about 40 minutes to complete for those receiving EMPOWER only (Time point 4, T4). Assessments will be completed using paper-and-pencil assessments, over the phone with research staff, or online (REDCap). The exit interview will be audio recorded and can be in person, over the phone, or over videoconference.

The EMPOWER arm includes 6 modules that are approximately 15-20 minutes each, all delivered by the same interventionist one-on-one in person or if needed, over the phone or video conference. The intervention can be completed in approximately 1.5 to 2 hours in a single sitting in the ICU, or modules can be completed in piecemeal if the surrogate decision-maker prefers or needs to stop because of, for example, the need to attend to the patient or speak with the medical team. If the intervention is completed in piecemeal, it is expected the intervention will occur over the course of 2-3 days, although scheduling will be flexible to not burden participants and be sensitive to needs such as bereavement and urgent medical situations. There are 2 booster sessions (approximately 1 hour each) that are conducted via telehealth medium such as phone or video call 2 and 4 weeks after the initial 6 modules are completed. If the patient dies before the 6 modules are completed, the interventionist will make a condolence call during which he/she will offer to continue the modules if the surrogate decision-maker is interested (during that call or at a separate time). If the surrogate decision-maker declines completion of the 6 modules, the interventionist will indicate that he/she will call again in 2 weeks to offer support and review what they have previously discussed. Due to the wide variety of

participant experiences and circumstances in the ICU, parts of the intervention may be omitted or amended at the discretion of the interventionist to meet the needs of the participant. The EMPOWER intervention is designed to be administered in the ICU, but to accommodate the varying needs of participants, may be administered in other private clinical settings on the campuses of the recruiting sites as well as via applications used for telehealth, such as but not limited to Webex or Zoom.

All participants who receive EMPOWER (both open trial and RCT cases) will be audio- and/or video-recorded for supervision and training purposes, with the participant's approval. They can opt out of video-recording and still participate, but audio-recording is mandatory.

EMPOWER is based on well-established cognitive-behavioral and acceptance-based techniques that aim to reduce maladaptive avoidance of distressing emotions. The EMPOWER interventionist will be compassionate and will attempt to provide validation of the surrogate decision-makers' experience; to teach tools for remaining present-focused; to explore the surrogate decision-maker's and the patient's wishes, values, and decision challenges; to increase their sense of acceptance and permission to experience challenging emotions; and to prepare them to cope with future distressing situations.

The primary outcome will be peritraumatic distress. We hypothesize that at post-intervention assessment, surrogate decision-makers who receive EMPOWER will have significantly lower symptoms of peritraumatic distress when compared to surrogate decision-makers who receive ICU enhanced usual care.

Secondary surrogate decision-maker outcomes will be surrogate decision-maker Prolonged Grief Disorder (PGD) symptom severity (either pre-loss/anticipatory or post-loss/bereavement grief) and experiential avoidance at one-month and three-month follow up. Exploratory surrogate decision-maker outcomes will be symptom severity of PTSD, depression, anxiety, and decision regret at one-month and three-month follow up. For both secondary and exploratory outcomes, we hypothesize that surrogate decision-makers who receive EMPOWER will have significantly lower symptoms compared to surrogate decision-makers who receive ICU enhanced usual care.

Patient outcomes will include ACP, intensity of care, and quality of life/death one-month post-baseline. We hypothesize that patients whose surrogate decision-makers receive EMPOWER will report better quality of life/quality of death with more value-concordant care compared to those whose surrogate decision-makers receive enhanced usual care.

In the event of patient death, the study team will mail either a handwritten or typed condolence card with a standardized message. This condolence card may not be mailed at the discretion of the principal investigators.

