- #1: Develop EMPOWER for surrogate decision-makers of critically ill patients who are at risk of becoming incapacitated and/or who are currently unable to make medical decisions. Key informants, including bereaved informal caregivers of ICU patients and clinicians, will be asked to evaluate the EMPOWER intervention manual to increase its potential tolerability, acceptability, and efficacy.
- **#2: Determine the feasibility, tolerability, acceptability, and preliminary effects of EMPOWER on surrogate mental health.** We hypothesize that revised EMPOWER will be feasible, tolerable, and acceptable. The intervention will also reduce peritraumatic distress post-intervention, and improve mental health outcomes at one-month and three-month follow up from post-intervention assessment compared to enhanced usual care.
- **#3:** Estimate the effects of EMPOWER on patient outcomes in the months following the baseline assessment. Patients who receive EMPOWER are expected to have higher rates of engagement in advance care planning (e.g., a DNR order completed), better surrogate-reported quality of life/quality of death, and more value-concordant care (measured through comparing intensity of care at end-of-life to surrogate perception of patient treatment preferences) compared to patients whose surrogates receive enhanced usual care.

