2.0 Objectives

Specific Aim #1:

Develop EMPOWER for surrogate decision-makers of critically ill ICU patients who are at risk of becoming incapacitated and/or who are currently unable to make medical decisions.

There are no hypotheses for this objective. Stakeholders, including bereaved ICU patient caregivers and clinicians, will be asked to evaluate the EMPOWER intervention manual to increase its potential tolerability, acceptability, and efficacy. Data from the open trial of 10 surrogate decision-makers will also identify tactical and measurement issues involved in the delivery and outcome measurements used in EMPOWER.

Specific Aim #2:

Determine feasibility, tolerability, acceptability, and preliminary effects of EMPOWER on surrogate decision-maker mental health.

Hypothesis #2:

Revised EMPOWER will be feasible, tolerable, acceptable. Those who are randomized to EMPOWER will have reduced peritraumatic distress at post-intervention assessment (T2). Those who are randomized to EMPOWER will have reduced symptoms of PTSD, prolonged grief disorder, anxiety, and depression, and less decisional regret and experiential avoidance at one-month and three-month follow up from baseline (T3 and T4).

Specific Aim #3:

Examine the effects of EMPOWER on patient outcomes, including intensity of care and quality of life/quality of

death, in the months following baseline assessment.

Hypothesis #3:

Patients whose surrogate decision-makers receive EMPOWER will have better quality of death (for patients who died), better quality of life (for patients who are still alive) and more value-concordant care compared to those whose surrogate decision-makers receive enhanced usual care at one-month (T3) and three-month (T4) follow up from post-intervention assessment.

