4.0 Informed Consent Process

Informed consent is a process, not a one-time event. During the informed consent process, the study staff obtaining consent will review the study in detail allowing for the participant (surrogate decision-maker, stakeholder, or patient) to interject with questions at any time during the discussion. It is extremely important that the participant has an opportunity to have his/her questions addressed as well as ample time to read the consent document and determine whether or not they would like to participate in the study. For consents occurring in-person, study staff and potential participants will review the consent form together. For consents occurring digitally, study staff will contact potential participants and provide them with a digital copy of the consent form in REDCap that they will able to simultaneously view virtually while speaking to the consenting professional. Attending physicians and fellows who are trained, IRB-approved members of the research team, such as but not limited to those working in the pediatric intensive care unit, may also obtain consent from surrogates and patients, including those under their care, using the procedures outlined in this section. Any reference to study personnel/staff in regard to recruitment/consenting procedures includes these physicians.

The main points that will be addressed by the study personnel obtaining informed consent include explaining why the current research study is being conducted, the sources of funding for the project and what purpose the proposed research serves. Additionally, the subject will be made aware who is responsible for conducting the research, what other sites are involved, as well as how subjects are selected for participation in the research.

The study staff will explain in explicit detail what will be asked of participant if he/she agrees to participate in the study and estimate the potential time commitment involved. The participant will know what his/her responsibilities will entail, what risks or benefits may be involved, and what potential costs could be incurred should they agree to participate. Study staff will underscore the importance placed upon maintaining participant confidentiality, as well as participant's rights while involved in the study, which includes the right to withdraw participation at any time during the research due to the fact that their participation is entirely voluntary in nature.

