5.1 Measures Used

Measures may be completed using hard copies, online (REDCap), or by RA interview, depending on the respondent's preference and research restrictions due to COVID-19. During the COVID-19 open trial, any hard copies will be mailed, digital copies will be emailed and RA interviews will occur over the phone or other telehealth medium.

Sociodemographic Characteristics:

Demographics: Surrogate decision-makers' will be asked in a self-report assessment occurring either in clinic or over the telephone their own and the patient's age (years), gender, race, education, mental health history, income, marital status, religious/spiritual beliefs, ACP knowledge/understanding, treatment preferences, prognostic understanding, and relationship with patient. Stakeholders will report on their own demographics.

Medical factors for Patients:

Patients' diagnoses (e.g., Stage IV pancreatic or NSCL cancer), reason for hospital/ICU admission, DNR/DNI order status, ACP items (including palliative care consultations), care plans obtained from the medical chart or ICU physicians and fellows, as well as clinically relevant symptoms related to patient incapacity, such as but not limited to, delirium. This information will be compiled as a medical chart abstraction and matched with surrogate-assessed patient treatment preferences assessed at T1 to create a measure of rates of value-concordant care. These medical factors, in addition to the CEQUEL ²³, will serve to measure the outcomes specified in Aim #3.

Psychosocial factors for Surrogate decision-makers:

Screener: Consists of items from 4 items from McGill Quality of Life¹⁹, two items from the Partner Dependency Scale ¹⁸, and two items from the Columbia Suicide Severity Rating Scale ²⁰.

Adult Surrogate Pre-intervention/ Baseline Assessment (T1): Psychiatric History, Demographics, and Treatment Preferences; Prolonged Grief Disorder (PG-12) Caregiver Version; ²⁴ ^{25,26}; Fear of Losing Loved Ones Scale (FOLLOS); Peritraumatic Distress Inventory (PDI) ²⁷; Peritraumatic Dissociative Experiences Questionnaire (PDEQ) ICU Version²⁸; Impact of ICU Events Scale-Revised (IES-R) ²⁹; Brief Experiential Avoidance Questionnaire (BEAQ); ³⁰State Trait Anxiety Inventory - State scale (STAI) ³¹; Patient Health

Questionnaire (PHQ-9); ³² Distress Tolerance Scale (DTS) ³³ revised version; Caregiver Self-Efficacy in the ICU Scale; Decision Regret Scale (DRS) – EMPOWER³⁴; Regret Assessment.

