Fears of Losing Loved Ones Scale (FOLLOS)	T1, Status dependent @ T2, T3, T4	Measures attachment-related distress associated with anticipatory grief. Items were developed by clinicians and an expert in psychometrics.
Caregiver Evaluation of the Quality of End-of-Life Scale (CEQUEL)	Status dependent @ T3, T4	Measures caregiver's subjective evaluation of the patient's quality of death. If administered at T3 due to patient death, will not be administered at T4.
CEQUEL-Revised	Status dependent @ T3, T4	Administered to caregivers whose patients are still living. Retains items measuring caregiver satisfaction with medical care for the patient, but removes questions regarding patient's death.
CEQUEL-Revised	Status dependent @ T3, T4	Administered to caregivers whose patients are still living. Retains items measuring caregiver satisfaction with medical care for the patient, but removes questions regarding patient's death.
Quality of Life/Death	Status dependent @ T3, T4	Measures caregiver's perception of the patient's most recent week of life (either their most recent week, or most recent week before death). If Quality of Death is administered at T3, it will not be administered again at T4. Items have been previously published upon and validated ² .

^{*}Refers to assessments for adult surrogate participants

Qualitative data:

All surrogate decision-makers will provide feedback on the intervention in a post-intervention satisfaction questionnaire at T2. Those assigned to the EMPOWER intervention will also participate in a qualitative exit interview at T4. Stakeholders will provide feedback on the intervention manual in self-report questionnaires, written form, and/or in-person interviews. Clinicians will provide information about the patient before recruitment occurs via the patient information form or discussion with research assistants.

5.2 Data Collection (Please find the details on data to be collected in 5.2)

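### Aim 3 words surrogate ratings as patient outcomes; because the rater is the treated person, an arm difference in them cannot by itself show patient benefit

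*Combined protocol and SAP*

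**What the plan says.** The documents describe the Aim 3 quality outcomes in two ways.

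**As patient outcomes**
- Section 5.2 (Study Design, Pilot Trials) hypothesises that "patients whose surrogate decision-makers receive EMPOWER will report better quality of life/quality of death".
- Section 2.0 (Objectives), Hypothesis #3, says patients "will have better quality of death (for patients who died), better quality of life (for patients who are still alive", with no mention of who rates.
- Section 6.1 (Data Analysis Plan), Specific Aim #3, regresses the patient's quality of life or of death on condition, again with no mention of the rater.

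**As surrogate ratings**
- Section 1.1 (Introduction), Aim #3, expects "better surrogate-reported quality of life/quality of death".
- Section 5.1 (Measures Used) describes the Quality of Life/Death items thus: "Measures caregiver's perception of the patient's most recent week of life". For CEQUEL it says: "Measures caregiver's subjective evaluation of the patient's quality of death". CEQUEL-R keeps the items on the caregiver's satisfaction with care. All three sit in the adult surrogate batteries at T3 and T4.

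Aim 3 also has outcomes from the medical record: DNR/DNI status, advance care planning items and care received. The last is matched with the preferences that the surrogate reports at T1 to give value-concordant care. Section 5.1 joins the two kinds of source: "These medical factors, in addition to the CEQUEL" are to measure Aim 3.

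**The concern.** EMPOWER is delivered to the surrogate, not to the patient. It aims to lower the surrogate's peritraumatic stress, grief and avoidance, and surrogate distress at T2 is the primary outcome. The same person then rates the patient's last week and the care given. If EMPOWER changes how the surrogate feels, the rating may move although nothing has changed for the patient.

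Read as sections 2.0, 5.2 and 6.1 are worded, such a difference would count as evidence that EMPOWER improves the patient's quality of life or death. The results are meant to support an application for a larger efficacy trial, so a mislabelled patient effect could carry into that trial's rationale and choice of endpoints.

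**Working it through.** **1. Who completes the forms.** Section 5.1 lists the instruments at the screener and at T1 to T4. All are completed by the surrogate, apart from the record abstraction. No quality-of-life form is given to patients, and a quality-of-death rating could not come from the patient in any case. The sentence in 5.2 therefore conflicts with 5.1 and with 1.1.

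**2. Whether the rater knows the arm.** The documents do not say so outright; it follows from the design. One arm gets six interventionist-led modules and two booster sessions; the other gets usual care with resource lists and an information packet. The COVID-19 open trial, which counts towards the 60, had no control arm. No masking of surrogates is described.

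**3. Whether the analysis can separate rater from patient.** Write the arm difference in the rating as

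D = P + B,

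where P is the change in the patient and B the change in the rater. The plan observes D only. It has no second rater who was not given the intervention. The T1 battery contains no Quality of Life or CEQUEL rating, so there is no baseline rating to adjust for. The Aim 3 analysis gives no sensitivity analysis and no limit on interpretation. One equation with two unknowns leaves P undetermined.

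**4. Which Aim 3 outcomes are outside this problem.** DNR/DNI status, planning items and care received come from the record. Value-concordance uses T1 preferences, taken before the intervention. None of these rests on a post-treatment surrogate rating.

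**5. Size.** The plan's only sizing figure is about 80% power for d = 0.75 at alpha 0.05. Two-sided, normal approximation:
- 30:30: 0.75/√(1/30 + 1/30) = 2.905; power Φ(2.905 − 1.960) = 82.8% (81.5% by the t test).
- 40:20: 0.75/√(1/40 + 1/20) = 2.739; power Φ(2.739 − 1.960) = 78.2% (76.8% by the t test).

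This figure is not stated for Aim 3, and the point does not depend on it.

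To size B one would need B = δ × ρ. Here δ is the surrogate-mood effect at T3/T4 in SD units, and ρ is the correlation of mood with the rating, given the patient's true state. The documents supply neither. For illustration only, assume P = 0, a continuous rating and all 60 surrogates rating:

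| δ (assumed) | ρ (assumed) | B (SD) | Two-sided rejection at 40:20 (nominal 5%) |
|---|---|---|---|
| 0.50 | 0.1 | 0.05 | 5.4% |
| 0.50 | 0.6 | 0.30 | 19.5% |
| 0.75 | 0.1 | 0.075 | 5.9% |
| 0.75 | 0.3 | 0.225 | 13.0% |
| 0.75 | 0.6 | 0.45 | 37.6% |

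Rejection is Φ(x − 1.960) + Φ(−x − 1.960) with x = B/√(1/40 + 1/20) = B/0.274. The range runs from almost nothing to severe, so it is not an estimate. Fewer raters (pediatric surrogates do not get these forms) would lower the rejection rates but not B.

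**The case against.** The best defence is that the rater is disclosed. The Introduction and the measures table both name the surrogate, and the wording in 5.2 is one loose sentence. This is also a proof-of-concept pilot, Aim 3 is not primary, and proxy rating is largely unavoidable: more than 85% of the patients in the team's earlier pilot could not communicate. All of that stands. It limits the weight of the point and means the measures should be kept. It does not remove the conflict in wording or the limit on what the ratings can show.

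A reader might go further in three ways that the documents do not support.

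- **That the chart outcomes are compromised as well.** Section 5.1 allows "care plans obtained from the medical chart or ICU physicians and fellows", and section 4.0 lets "Attending physicians and fellows who are trained, IRB-approved members of the research team" obtain consent, including for patients under their care. But 5.1 does not say that clinician information is verbal or unrecorded. Consent comes before screening, T1 and the intervention, so obtaining it does not in itself reveal the arm in the RCT. What remains is that no section keeps the arm from the abstractor, which justifies a precaution but does not show a bias.
- **That Aim 3 merely repeats Aim 2.** The Aim 2 scales cover the surrogate's own symptoms, avoidance and regret. The Aim 3 forms ask about the patient's last week and care. A shared informant does not make them one construct. Nor does the plan say that EMPOWER trains acceptance of the patient's condition; section 5.2 speaks of the surrogate's own emotions.
- **That the bias has a known size, such as 0.75 × 0.3 to 0.75 × 0.5, or about 0.22 to 0.38 SD.** The 0.75 is a detectable effect, whereas the primary outcome is at T2 and the ratings come at T3 and T4. The correlation is assumed. A raw correlation would also contain real signal, since sicker patients may have more distressed surrogates. The planned analysis is logistic, so an SD shift is not on its scale.

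**Conclusion.** The point holds for Quality of Life/Death, CEQUEL and CEQUEL-R, and only for those. Sections 2.0, 5.2 and 6.1 state as a patient effect what 1.1 and 5.1 show to be a surrogate rating. The rater is the treated person, so an arm difference could reflect a change in the rater and cannot by itself support a conclusion of patient benefit.

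The size of the bias cannot be obtained from the documents. Its direction is an assumption too: it would favour EMPOWER if less distressed surrogates rate the patient more kindly. That surrogates know their arm is inferred from the visible difference between the arms and the absence of any described masking. For a non-primary aim of a pilot, this is worth correcting because correction is cheap and the results feed the next trial; it is no reason to drop the measures.

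**What to change.** **Wording.** In 2.0 (Hypothesis #3), 5.2 and 6.1 (Specific Aim #3), call these outcomes surrogate-perceived quality of life or death, in line with 1.1, and remove the statement in 5.2 that patients report them.

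**Basis for patient-level conclusions.** State in 6.1 that any patient-level conclusion of Aim 3 rests on the chart-derived outcomes: DNR and other planning items, intensity of care, and value-concordant care matched to T1 preferences. Take these from dated chart entries, abstracted by existing staff who are given the study ID without the arm where feasible.

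Adjusting the surrogate ratings for post-treatment mood would not solve the problem, because treatment itself affects mood.

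**Cost.** Protocol wording and one abstraction instruction; no new participants or visits. The downsides are real:
- The Aim 3 claim becomes narrower.
- Care-plan items not entered in the chart would be missing.
- Dyads without chart data drop out of the patient-level conclusion, and their number must be reported. They include surrogates from outside hospitals, who report the patient's general health themselves (5.2), and dyads in which the patient's record is not accessed (4.0).
- Masking cannot fully protect the COVID-19 open-trial cases: all received EMPOWER, and chart dates would suggest the phase.
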